5.1.1 Part 1 IPdR Dose Escalation Schedule

Original Design (no longer active, reference only): An initial single patient dose escalation of IPdR will be conducted in Part 1. The starting dose is 150 mg (dose level 1A). A 100% dose escalation will be used until a treatment-related Grade 2+ toxicity or otherwise a DLT (as defined in Section 5.2) is observed. If a grade 2+ toxicity or DLT is observed in a patient, two additional patients will then be entered at this dose level. Subsequent steps would be guided by the occurrence of any grade 2+ toxicity or DLT in the cohort of 3 patients (including the initial single patient) with rules as states below:

- a. If only 1 of the 3 patients experiences Grade 2+ toxicity and this is not a DLT, then the design will stay with Part 1.
- b. If any of the 3 patients experience a DLT or 2+ patients experience Grade 2+ toxicity, then the design will switch to Part 2.
 - i. If only 1 of 3 patients has experienced a DLT or 2+ patients experience Grade 2+ toxicity, the dose level in Part 2 will be the same and that dose level will be expanded to 6 patients (3 more patients)
 - ii. If 2+ patients have experienced a DLT, then the dose will be de-escalated on Part 2 to half of the current dose (same as one level lower dose of part 1).

If dose level 1A results in 2 DLTs, then the trial will be closed as no maximum tolerated dose will have been identified. Dose Increment Schedule will be as shown in table 4 after 4 weeks of follow up of the prior cohort to assess acute, but delayed, toxicity).

Design Amendment:

The above text in section 5.1.1 is how the study was originally designed. However, to speed up accrual at the recommendation of CTEP medical officer and based on updated results of study 8866 and 9882 demonstrating safety of the drug IPdR at higher doses both alone and in combination with radiation (section 2.4) it was recommended to stop accrual to part 1 of the study at dose level 1B and open Part 2 at dose level 2A (1200mg), following the modified 3+3 design outlined in the Part 2 below.

Table 4: Part 1 IPdR Dose Increment Schedule

Dose Level	Dose (mg)	Multiple of starting dose	% increase above previous dose level
1A	150	1x	N/A
1B	300	2x	100

5.1.2 Part 2 IPdR Dose Escalation Schedule

Original Design (no longer active, reference only): In Part 2 of this Phase 1 protocol, a standard cohort 3+3 design (see table 5) will be used where up to three patients will be accrued to a given dose level (starting with no increase of the final Part 1 dose and escalating per table 6). After each cohort has been accrued the study will temporarily close to assess DLT status of each patient. The decisions to re-open, and at what level to re-open, are on the following:

- If DLT is not seen in any of the 3 patients, 3 new patients will be accrued and treated at the next higher dose level. If DLT is seen in 2 or 3 of 3 patients treated at a given dose level, then the MTD has been exceeded and the next 3 patients will be treated at the next lower dose level (unless there have already been 6 accrued to that lower level).
- If DLT is seen in 1 of 3 patients treated at a given dose level, up to 3 additional patients will be enrolled and treated at the same dose level. If DLT is seen in at least one of these additional patients (at least 2 of 6), the MTD will have been exceeded. If DLT is not seen in any of the three additional patients, 3 new patients will be accrued and treated at the next higher dose level.
- After enrolling 6 patients on a specific dose level, if DLT is observed in at least 2 of 6 patients, then the MTD will have been exceeded and defined as the previous dose level unless only 3 patients were treated at the lower dose level. In that case, 3 additional patients will be treated at this lower dose level such that a total of 6 patients are treated at the MTD to more fully assess the toxicities associated with the MTD.
- If a patient fails to complete the initial course of therapy (cycle 1) for reasons other than dose-limiting toxicity defined adverse events, the patient will be regarded as uninformative in regard to the MTD goal and an additional patient will be treated at the current dose level; however, all toxicity information will be utilized in the analysis.

The MTD is defined as the dose below which 2 or more of 6 patients experience dose-limiting toxicity.

Design Amendment #1 (to be superceded by Design amendment #2 below):

In Part 2 of this Phase 1 protocol, a modified cohort 3+3 design (see table 5) will be used where up to three patients will be accrued to a given dose level (starting with 1200 mg IPdR dose and escalating per table 6). After each cohort has been accrued the study will temporarily close to assess DLT status of each patient. The decisions to re-open, and at what level to re-open, are on the following:

- If DLT is not seen in any of the 3 patients, 3 new patients will be accrued and treated at the next higher dose level.
- If DLT is seen in 3 of 3 patients treated at a given dose level, then the maximally tolerated dose (MTD) has been exceeded and the next 3 patients will be treated at the next lower dose level such that a total of 6 patients are

treated to more fully assess the toxicities (unless there have already been 6 accrued to that lower level which will then be labeled as the MTD and the study will proceed to the expansion cohort).

- If DLT is seen in 1 or 2 of 3 patients treated at a given dose level, up to 3 additional patients will be enrolled and treated at the same dose level. Including the three additional patients, following rule will be applied:
 - DLT is seen in 1 of the total 6 patients, proceed to the next higher dose level.
 - DLT is seen in 2 of the total 6 patients, then dose escalation is stopped, and this dose level is declared the MTD. The study will proceed to the expansion phase.
 - DLT is seen in 3 or more of the 6 patients have DLT, the MTD will have been exceeded and the next 3 patients will be treated at the next lower dose level such that a total of 6 patients are treated to more fully assess the toxicities (unless there have already been 6 accrued to that lower level which will then be labeled as the MTD and the study will proceed to the expansion cohort).
- If a patient fails to complete the initial course of therapy (cycle 1) for reasons other than dose-limiting toxicity defined adverse events, the patient will be regarded as uninformative in regard to the MTD goal and an additional patient will be treated at the current dose level; however, all toxicity information will be utilized in the analysis.
- In the event MTD is exceeded in part 2 at the first dose level (1200mg), the next lower dose of IPdR will be 900 mg. If MTD is exceeded even at 900 mg, then a dose level of 600 mg will be tested. At both these levels, a minimum of 6 patients will be evaluated.

The MTD is defined as the highest dose that has fewer than 3 (out of 6) patients experiencing dose-limiting toxicity.

Table 5: Part 2 IPdR Dose Increment Schedule

Dose level	Dose (mg)
2A*	1200
2B	1800
2C	2400

* See text in 5.1.2 for the scenario MTD is exceeded at 1200 mg dose.

Table 6: Part 2 Dose Escalation Decision Rules

Number of Patients with DLT at a Given Dose Level	Escalation Decision Rule
0 out of 3	Enter 3 patients at the next dose level. If this is the highest dose-level, then accrue additional 3 patients at the dose-level.
3 out of 3	MTD is exceeded and the dose escalation will be stopped. This dose level will be declared the maximally administered dose (highest dose administered). Three (3) additional patients will be entered at the next lowest dose level such that a total of 6 patients are treated to more fully assess the toxicities (unless there have already been 6 accrued to that lower level which will then be labeled as the MTD and the study will proceed to the expansion cohort).
1 or 2 out of 3	Enter 3 more patients at this dose level. 
• DLT is seen in 1 of the total 6 patients, proceed to the next higher dose level.• DLT is seen in 2 of the total 6 patients, then dose escalation is stopped, and this dose level is declared the maximally tolerated dose (MTD). The study will proceed to the expansion phase.• DLT is seen in 3 or more of the total 6 patients, then MTD is exceeded and the dose escalation is stopped. This dose level is declared maximally administered dose (highest dose administered). Three (3) additional patients will be entered at the next lowest dose level such that a total of 6 patients are treated to more fully assess the toxicities (unless there have already been 6 accrued to that lower level which will then be labeled as the MTD and the study will proceed to the expansion cohort).
≤ 2 out of 6 at highest dose level below the maximally administered dose	This is the maximally tolerated dose, MTD.

Design Amendment #2:

As described in section 2.5.2, after accruing one patient at the dose-level 2B of table 5, the study is being amended to close the dose-level 2B and re-open 2A (1200 mg) to enroll 3 additional patients. The results of 6 total patients at dose-level 2A (1200 mg) will be evaluated per the table 7 below

Table 7: Part 2 Dose Escalation Decision Rules

Number of Patients with DLT at a Given Dose Level	Escalation Decision Rule
0 out of 3 (0 out of 6 patients)	This dose-level is declared the recommended phase 2 dose (RP2D). The study will proceed to the expansion phase.
1 or 2 out of 3 (total 1 or 2 out of 6 patients)	This dose level is declared the RP2D. The study will proceed to the expansion phase.
3 out of 3 (total 3 out of 6 patients)	MTD is exceeded and the dose level will be declared the maximally administered dose (highest dose administered). Three (3) additional patients will be entered at the next lowest dose level such that a total of 6 patients are treated to more fully assess the toxicities (unless there have already been 6 accrued to that lower level which will then be labeled as the RP2D and the study will proceed to the expansion cohort).

5.1.3 Expansion Cohort

An expansion cohort of 10 additional patients will be treated at the RP2D to confirm safety and further test the exploratory biomarkers. If after 16 patients have been treated at the RP2D (6 in part 2 and 10 in the expansion cohort), there are at most 5 patients with a DLT (31.25%) then this dose will remain as the RP2D. If there are more than 5, then the next lower dose will be RP2D.

Based on the design proposed, the highest acceptable probability of DLT is 31.25% (5 or less events in 16 patients), with the target expected probability of DLT of 20-30% (of which 18-20% is expected from WBRT alone).

The following table shows some of the operating characteristics for the current design under a number of possible DLT rates. For each given dose, the table displays the likelihood of increasing to the next dose and the probability of having at most 5 patients with DLTs (out of 16). For example, if the true DLT rate is 0.4 for a given dose level, there is only a 31% chance of accruing above that dose level. If on the other hand, the true DLT rate for a given dose is 0.3 (close to target acceptable rate) and if this dose level is determined to be the MTD during the dose finding stage, then there is a 66.6% chance of having 5 or fewer patients with DLT (out of 16).

DLT Rate	Probability of dose escalation	Probability of having at most 5 Patients with DLT (out of 16)
0.1	0.906	0.997
0.2	0.709	0.918

0.3	0.494	0.660
0.4	0.309	0.329
0.5	0.172	0.105
0.6	0.082	0.019

When a patient at any site is undergoing the study treatment or is pending DLT assessment, the PI of the study (or representative) will regularly meet (in person, by teleconference or by email) with the study statistician and the participating site's study team to review any updates regarding potential adverse events being experienced by the study subject from the WBRT (or any other extracranial RT, if applicable). If necessary, clinical inputs from the treating physician and the participating site PI will be obtained to assist in the decision regarding the adverse event being labeled as a DLT.

Unexpected severe late neurologic radiation toxicity or extra-cranial radiation toxicity will be recorded as a secondary end-point. These events will be reviewed by the independent DSMB who will be charged with considering cessation of the trial if the long term/delayed (6 months) \geq grade 3 symptomatic neurotoxicity or other extra-cranial radiation toxicity is $> 20\%$.

Use of other therapies post-DLT assessments which might impact neurological functioning (including but not limited to immunotherapy, for which safety data of immune-related neurological adverse events after WBRT is relatively limited) will be considered for this decision.

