12.1 Study Oversight

This protocol is monitored at several levels, as described in this section. The Protocol Principal Investigator is responsible for monitoring the conduct and progress of the clinical trial, including the ongoing review of accrual, patient-specific clinical and laboratory data, and routine and serious adverse events; reporting of expedited adverse events; and accumulation of reported adverse events from other trials testing the same drug(s). The Protocol Principal Investigator and statistician have access to the data at all times through the CTMS web-based reporting portal.

For the Phase 1 portion of this study, all decisions regarding dose escalation/expansion/de-escalation require sign-off by the Protocol Principal Investigator through the CTMS/IWRS. In addition, for the Phase 1 portion, the Protocol Principal Investigator will have at least monthly, or more frequently, conference calls with the Study Investigators and the CTEP Medical Officer(s) to review accrual, progress, and adverse events and unanticipated problems.

All Study Investigators at participating sites who register/enroll patients on a given protocol are responsible for timely submission of data via Medidata Rave and timely reporting of adverse events for that particular study. This includes timely review of data collected on the electronic CRFs submitted via Medidata Rave.

All studies are also reviewed in accordance with the enrolling institution's data safety monitoring plan.

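### The expansion cohort's more-than-5-DLT rule is read only at 16 patients, and no provision in force requires accrual to stop once a 6th DLT has settled the result

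*Combined protocol and SAP*

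**What the plan says.** Table 7 in Section 5.1.2 (Design Amendment #2) governs entry to the expansion. A dose with 0 DLTs in 6 patients enters, and so does one in the row "1 or 2 out of 3 (total 1 or 2 out of 6 patients"), where the instruction is "This dose level is declared the RP2D. The study will proceed to the expansion phase".

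Section 5.1.3 then provides: "An expansion cohort of 10 additional patients will be treated at the RP2D to confirm safety and further test the exploratory biomarkers". The decision is tied to the full count of 16: "If after 16 patients have been treated at the RP2D (6 in part 2 and 10 in the expansion cohort"). The dose is kept if "there are at most 5 patients with a DLT (31.25%) then this dose will remain as the RP2D", and otherwise "If there are more than 5, then the next lower dose will be RP2D". The same section states the intent: "the highest acceptable probability of DLT is 31.25% (5 or less events in 16 patients), with the target expected probability of DLT of 20-30"%.

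Other provisions bear on stopping:

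- **Section 5.1.3, review meetings.** While any patient is on treatment or awaiting DLT assessment, the study PI meets regularly with the statistician and the site team.
- **Section 5.1.3, DSMB.** The DSMB considers ending the trial if late (6-month) grade 3 or higher toxicity exceeds 20%.
- **Section 12.1.** Calls with the CTEP Medical Officer take place at least monthly, and "all decisions regarding dose escalation/expansion/de-escalation require sign-off by the Protocol Principal Investigator through the CTMS/IWRS".
- **Section 13.2.** The accrual-time estimate mentions closing the study for DLT evaluation, without saying when or on what count.
- **Section 5.1.2, Design Amendment #1.** A pause after each cohort is described for dose finding, in text marked as superseded.
- **Section 5.1.** Observation to Day 35 is required before enrolling at the next dose level. Expansion patients stay at the same level.

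**The concern.** Once six patients at the RP2D have had a DLT, no later outcome can bring the total back to five. Any patient enrolled after that is treated at a dose the trial's own criterion has already rejected, and that patient's result cannot alter the RP2D decision.

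None of the provisions above turns the 6th DLT into a stop. The DSMB trigger concerns a different and later endpoint. The meetings, calls and sign-off carry no acute-DLT number. The closure in Section 13.2 has no timing or count. What is at stake is avoidable exposure of patients. The RP2D conclusion itself is not affected.

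**Working it through.** **Inputs.** 6 + 10 = 16 patients, with rejection at 6 or more DLTs (5.1.3). Entry to expansion requires at most 2 DLTs in 6 (Table 7). 0 of 3 DLTs have been seen at 1200 mg (Synopsis; 2.5.2). The DLT window runs to Day 35 (5.1). Assumed accrual is 1-2 patients per month (13.2).

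**The plan's own figures.** P(at most 5 of 16) from the binomial at rates 0.1 to 0.6 is 0.9967, 0.9183, 0.6598, 0.3288, 0.1051 and 0.0191. This agrees with the 5.1.3 table. (The text beside the table gives 66.6% at 0.3; the table's 0.660 is the correct value.)

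**Earliest crossing.** With 2 of 6 DLTs on entry, four consecutive DLTs put the 6th on patient 6 + 4 = 10, leaving 16 − 10 = 6 patients. With 1 or 0 on entry the maximum left is 5 or 4.

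**Model.** Patients are independent with DLT probability p, and 5.1.3 is taken to apply the Section 5.2 DLT definition to the expansion. Let d = 0, 1, 2 be the DLTs in patients 4-6, with weights w_d proportional to C(3,d) p^d (1−p)^(3−d), rescaled to sum to 1. Let K be the expansion patient on whom the 6th DLT falls. Then P(K ≤ m) = Σ w_d · P(Bin(m,p) ≥ 6−d).

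- 6th DLT before the last patient: P(K ≤ 9).
- Expected number still untreated, over all trials that enter expansion: Σ P(K ≤ m) for m = 1 to 9.
- Someone spared when two further patients are already on treatment: P(K ≤ 7).

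**Worked case, p = 0.4.** The weights are 0.216, 0.432 and 0.288 divided by 0.936, that is 0.2308, 0.4615 and 0.3077.

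- P(K ≤ 9) = 0.2308×0.0994 + 0.4615×0.2666 + 0.3077×0.5174 = 0.305.
- P(K ≤ 7) = 0.2308×0.0188 + 0.4615×0.0963 + 0.3077×0.2898 = 0.138.

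**At p = 0.2.** P(K ≤ 9) = 0.5161×0.00307 + 0.3871×0.01958 + 0.0968×0.08564 = 0.01745.

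| True DLT rate | Rule failed by patient 16 | 6th DLT before last patient | Expected untreated, all trials | Someone spared, two pending |
|---|---|---|---|---|
| 0.2 | 2.8% | 1.7% | 0.04 | 0.5% |
| 0.3 | 15% | 11% | 0.24 | 3.9% |
| 0.4 | 40% | 31% | 0.77 | 14% |
| 0.5 | 68% | 57% | 1.7 | 32% |
| 0.6 | 88% | 81% | 2.7 | 56% |

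**Why two pending is plausible.** 35 days is about 1.15 months. At 1-2 patients per month, roughly 1.2 to 2.3 patients enrol within one DLT window.

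**Probability of the worst case.** w_2·p⁴ is 0.1942×0.0081 = 0.16% at p = 0.3 and 0.3077×0.0256 = 0.8% at p = 0.4.

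**Sensitivity.** If all six Part 2 outcomes are treated as random, given at most 2 DLTs, the early-crossing chances are 3.3%, 16%, 40%, 66% and 86%.

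**The case against.** The strongest reply is that the trial is closely supervised and that the 16-patient sentence fixes a final classification without forbidding an earlier stop. Beyond the meetings, calls and sign-off, Section 7.3.3 calls for 24-hour notice of grade 3-5 serious events. Section 2.5.2 shows supervision at work: level 2B was closed after a single patient, without a numerical rule requiring it. At the target DLT rate early crossing is uncommon, and patients already on treatment reduce the benefit further. No estimate, error rate or RP2D decision changes.

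Most of this stands, and it limits how serious the point is. A reader might infer that the plan obliges sites to keep enrolling at a failed dose, or that it makes continued enrolment likely. The documents support neither: a discretionary stop is available throughout, and past conduct suggests it would be used. What remains is that a limit defining failure on the primary endpoint is left to judgement at the moment it is crossed, although writing it down would cost very little.

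A reader might also want registration held at 5 DLTs while others are pending. The documents do not support making that mandatory. Five of 16 is an acceptable result under 5.1.3, so the hold would interrupt trials that go on to pass, and Section 2.5.1 names blocked slots during DLT assessment as a barrier to accrual.

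**Conclusion.** The gap is real and modest. As written, up to 6 patients could be enrolled after the rule has already failed, but that extreme has a probability below 1% at rates up to 0.4. Averaged over all trials that enter expansion, 0.04 to 0.24 patients remain untreated at the 6th DLT for rates of 0.2 to 0.3, rising to 2.7 at 0.6. These figures assume that each DLT is known at once and that patients are independent; reporting delay lowers them, as the two-pending column shows. The benefit is concentrated at rates above the protocol's 31.25% ceiling, where protection matters most. This is a recommended, inexpensive safety improvement and not a defect that invalidates the design.

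**What to change.** Add one sentence to Section 5.1.3: accrual at the RP2D stops once a 6th patient treated at that dose, counting Part 2 and expansion together, has a confirmed DLT, and the existing more-than-5 outcome is then declared without enrolling the remaining patients. The threshold is the protocol's own, and the decision is the same in every sequence of outcomes. A mandatory IWRS hold at 5 DLTs is not part of this change.

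The costs fall only on a dose that has failed:

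- Fewer patients contribute to the toxicity confidence interval.
- Some biomarker patients may be lost. Section 9.2.2 takes granulocyte samples from the first 6 expansion patients, so at most 6 − 4 = 2 are lost, and none if the 6th DLT falls on the 6th expansion patient or later.
- The crude DLT proportion after an early stop is biased upward, and the report should say so.

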13. STATISTICAL CONSIDERATIONS

13.1 Study Design/Endpoints – Determination of the Maximum Tolerated Dose

The primary endpoint of this study is to determine the RP2D dose of daily oral IPdR administered alone for 7 days and then concurrently with conventionally fractionated whole brain radiation therapy (WBRT) for 3 weeks in patients with brain metastases. In order to determine the RP2D, an expansion cohort will be utilized, which is outlined in detail in sections 5.1.3. Dose limiting toxicity (DLT) is fully defined in section 5.2.

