Till date (December 2019), 2 patients have been accrued in part 1 (1+1), 3 patients at dose-level 2A and 1 patient at dose-level 2B. In the current proposed design amendment #7, since dose-level 2B is being stopped with one patient and dose level 2A will be re-opened for additional 3 patients, the expected accrual in the two parts will range from 9 (2+7) to 15 (2+7+6) patients. Ten patients will be accrued at the RP2D in the expansion cohort to help narrow the confidence interval on the estimate of incidence of toxicity at the RP2D which makes the range of accrual between 19 and 25. The maximum accrual will be 25 patients. Up to a total of six patients in the expansion cohort will be analyzed for the %IUDR-DNA cellular incorporation in circulating granulocytes and tumor once RP2D has been determined.

Assuming an accrual rate of 1-2 patients per month, for a minimal accrual of 18 patients

will require approximately 18-24 months. Additionally the study will close for evaluation of DLT leading to a total estimated study time of 30 months

Both men and women of all races and ethnic groups, when appropriate, will be eligible for these studies. Subject selection is equitable if they meet the inclusion and exclusion criteria. In conformance with the National Institutes of Health (NIH) Revitalization Act of 1993 (amended in October, 2001) with regard to inclusion of women and minorities in clinical research, possible interaction between race/ethnicity and treatment have been considered. Based on the historical number of brain metastases patients who receive WBRT per month at the University of Maryland and Mayo Clinic, there are expected to be approximately 15% of participants classified as minorities by race and 50% of participants to be female.

PLANNED ENROLLMENT REPORT

Racial Categories	Ethnic Categories				Total
	Not Hispanic or Latino		Hispanic or Latino		
	Female	Male	Female	Male	
American Indian/ Alaska Native	0	1	0	0	1
Asian	1	1	0	0	2
Native Hawaiian or Other Pacific Islander	0	0	0	0	0
Black or African American	1	2	1	0	4
White	19	19	1	1	40
More Than One Race	0	0	0	0	0
Total	21	23	2	1	47

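### If the expansion at 1200 mg fails, section 5.1.3 makes the next lower dose (most naturally 900 mg) the RP2D without requiring any patient to be evaluated there with WBRT

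*Combined protocol and SAP*

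**What the plan says.** Section 13.1 makes the expansion stage part of the primary endpoint: "In order to determine the RP2D, an expansion cohort will be utilized, which is outlined in detail in sections 5.1.3". In section 5.1.3, the dose stays the RP2D with at most 5 DLTs in 16 patients (6 from Part 2 plus 10 in expansion). Otherwise: "If there are more than 5, then the next lower dose will be RP2D".

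The active dose table (Table 5, section 5.1.2) lists 1200, 1800 and 2400 mg and nothing lower. Its footnote reads "See text in 5.1.2 for the scenario MTD is exceeded at 1200 mg dose". The text it points to is the last bullet of Design Amendment #1. That bullet says "the next lower dose of IPdR will be 900 mg" and adds "At both these levels, a minimum of 6 patients will be evaluated". It applies when 1200 mg fails in Part 2, and it sits under the heading "Design Amendment #1 (to be superceded by Design amendment #2 below".

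Table 7, under Design Amendment #2, covers failure at the six-patient stage: "Three (3) additional patients will be entered at the next lowest dose level such that a total of 6 patients are treated". Section 13.2 budgets for that step: "the expected accrual in the two parts will range from 9 (2+7) to 15 (2+7+6) patients".

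By the December 2019 statement in section 13.2, two patients had been treated in Part 1 (one each at 150 and 300 mg), three at 1200 mg and one at 1800 mg.

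**The concern.** The two active rules point in opposite directions. Failure at 1200 mg in six patients leads to a six-patient evaluation of the next dose down. Failure in sixteen patients, which is stronger evidence of toxicity, leads straight to an RP2D label with no evaluation.

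The older bullet that names 900 mg also set a six-patient minimum, but that minimum does not clearly carry over. Its heading marks it as to be superseded. Its trigger is failure in Part 2, and section 5.1.3 counts the Part 2 patients separately from the expansion patients.

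At stake is the primary result. On this branch, followed as written, the trial would report an RP2D for IPdR with WBRT at a dose for which it has no DLT rate. A phase 2 trial could start from that dose.

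**Working it through.** **1. Patients at 900 mg.** From sections 2.5.1 and 13.2: 150 mg, 1; 300 mg, 1; 1200 mg, 3; 1800 mg, 1. The total is 6, with none at 900 mg.

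**2. The plan's own table.** Section 5.1.3 gives the probability of at most 5 DLTs in 16 as 0.918 at a true rate of 0.20 and 0.660 at 0.30. The exact binomial P(Bin(16, p) ≤ 5) gives 0.9183 and 0.6598, so the table is reproduced. The complements, 8.2% and 34.0%, are the chances of failing before any data are seen.

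**3. The chance of the branch from here.** Two facts change those figures. Section 2.5.2 reports no DLT in the first three patients at 1200 mg. Table 7 also lets 1200 mg into expansion only if at most 2 of the next 3 have a DLT. Let x be the number of DLTs in those next 3. The branch needs more than 5 − x DLTs in the 10 expansion patients:

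P(branch) = Σ (x = 0, 1, 2) P(Bin(3, p) = x) × P(Bin(10, p) > 5 − x) ÷ P(Bin(3, p) ≤ 2)

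At p = 0.30: (0.343 × 0.0473 + 0.441 × 0.1503 + 0.189 × 0.3504) ÷ 0.973 = 0.1487 ÷ 0.973 = 0.153.

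| True DLT rate at 1200 mg | P(branch) |
|---|---|
| 0.10 | 0.1% |
| 0.15 | 0.7% |
| 0.20 | 2.8% |
| 0.25 | 7.4% |
| 0.30 | 15.3% |
| 0.3125 (the plan's limit) | 17.8% |
| 0.40 (above the limit) | 39.8% |

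The rates 0.20 to 0.30 are the plan's target range. The rates 0.10 and 0.15 are assumptions, included because the true rate may be below target. The 18% WBRT figure in section 2.5.1 counts any grade 3 or worse event possibly related to treatment, and the DLT definition in section 5.2 is narrower.

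**4. What the 1200 mg data would say about 900 mg.** The branch means at least 6 of 16 with a DLT, or 37.5%. If toxicity does not decrease as the dose rises, that is an upper-side reference for 900 mg. It lies above the 31.25% limit, so it cannot show that 900 mg is acceptable. Section 5.1.3 also expects 18–20% DLTs from WBRT alone, a part that less IPdR would not remove.

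**5. Room for an evaluation.** Part 1 (2) + 1200 and 1800 mg in Part 2 (6 + 1 = 7) + expansion (10) + six at 900 mg = 2 + 7 + 10 + 6 = 25, the stated maximum.

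**The case against.** The strongest reply is that the six-patient standard is already in the protocol. The dose name and the minimum stand in one bullet, and it looks selective to take the first and set aside the second. This stands in part. The sponsor may well intend the minimum to apply, and 900 mg is itself an inference. But if the bullet is dead, the next lower dose actually given is 300 mg, with one patient, which is no better supported.

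Second, 900 mg is not without evidence. The completed GI-cancer trial (section 2.4.3.2) gave it on the same 28-day schedule with 37.5 Gy in 15 fractions, and saw no IPdR-related toxicity of grade 2 or higher at that dose. Because section 5.2 also counts grade 4 or worse non-neurologic toxicity, with a limited exception, that trial does inform the systemic part of the DLT. The 16 patients at 1200 mg help too, and stepping down is the cautious direction. All of this stands. The GI trial, however, did not irradiate the brain, so it says nothing about neurologic DLTs with WBRT.

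Third, the label would not be purely mechanical. Section 12.1 requires Principal Investigator sign-off on de-escalation and at least monthly calls with the CTEP Medical Officer(s). Section 5.2 lets the final RP2D decision weigh toxicity from extracranial palliative radiotherapy. These safeguards make an automatic label less likely, but none sets a minimum number of patients.

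**Conclusion.** The concern holds as a gap in the primary-endpoint rule that should be fixed. Section 5.1.3 requires no evaluation at the fallback dose, and this conflicts with Table 7.

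Its size is modest: 2.8% to 15.3% across the plan's target range, and under 1% at a true rate of 0.15 or below. These figures assume independent patients with a common DLT rate, 0/3 so far at 1200 mg, and the six-patient rule passed. The zero count at 900 mg is as of December 2019.

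A reader might infer that 900 mg would be adopted with no relevant evidence, or that the label would be automatic. The documents support neither: the GI trial and the 1200 mg patients bear on tolerability, and sign-off and review are in place. A reader might also take 34% at a rate of 0.30 from the plan's table. That ignores the three patients already treated without a DLT and the rule for entering expansion. What is missing is narrower: a DLT rate for 900 mg with WBRT, and a stated minimum number of patients to obtain it.

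**What to change.** In section 5.1.3, name 900 mg as the dose below 1200 mg and replace the quoted sentence with:

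> If there are more than 5, 1200 mg is exceeded. 900 mg is not labelled RP2D until 6 patients have been evaluated there with WBRT and at most 2 have a DLT (the Table 7 limit); otherwise the trial reports that 1200 mg was exceeded and 900 mg is provisional only.

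The provisional label is meant for a cohort that cannot be filled. If three or more of the six have a DLT, the report should say that 900 mg also passed the limit.

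In Table 7, change the three additional patients to the number needed to give six, since three added to none is not six.

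The cost is wording only unless the branch occurs. It would then take up to 6 patients, at 1–2 per month about 3–6 months, plus the 35-day DLT window. They fit within 25 only if no patient needs replacing. If places run out, 900 mg is reported as provisional, so the maximum need not rise.

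Six patients give a coarse check. The limit of 2 in 6 rejects a dose with a true rate of 0.20, 0.25 or 0.30 in 9.9%, 16.9% or 25.6% of cases, from P(Bin(6, p) > 2), and passes a dose with a true rate of 0.40 in 54%. After 0, 1 or 2 DLTs the exact one-sided 95% upper limit is 39%, 58% or 73%. It is, however, the protocol's own standard for the same decision one stage earlier.
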